### **Recording and Reporting Adverse Events – Investigator & Sponsor Responsibilities**

#### Recording and Reporting Adverse Events - Investigator Responsibilities

The Investigator will:

- Record protocol required AE's together with an assessment as recorded in the Adverse Event Case Report Forms;
- Supply Wright Medical, upon their request, with any additional information related to the safety reporting of a particular AE

#### Recording and Reporting Adverse Events - Wright Medical Responsibilities

Wright Medical is responsible for the classification of AEs and ongoing safety evaluation of the study and will:

• review the Investigator's assessment of all AEs; determine and document, in writing, the seriousness of the adverse event and relationship of the adverse event to the implanted components.

In case of disagreement between Wright Medical and the Investigator, Wright Medical shall:

- communicate both opinions to concerned parties; and
- as required, ensure that the IRB/EC/REC and regulatory authorities are informed or significant new information involving the product during the study.

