#### Serious Adverse Event (SAE)

An adverse event (AE) or suspected adverse reaction is considered "serious" if, in the view of either the investigator or sponsor, it results in any of the following outcomes:

- death, or
- a life-threatening adverse event, or
- inpatient hospitalization or prolongation of existing hospitalization, or
- a persistent or significant incapacity or substantial disruption of the ability to conduct normal life functions

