#### 1. Adverse Evets

Adverse Event (AE) is defined as any untoward medical occurrence, unintended disease or injury, or untoward clinical signs (including abnormal laboratory findings) in subjects, users, or other persons, whether or not related to the investigational medical device. All adverse events shall be reported in an interim and/or final report of the clinical investigation. Frequency of these complications will be summarized by according to Preferred Term (PT) and System Organ Class (SOC) using Medical Dictionary for Regulatory Affairs (MedDRA 18.0).

The Investigator will follow up subjects who experience an AE until it is either resolved, determined to be chronic, stable, or, until the subject's participation in the study ends. Prior to completion of the study, the Investigator will complete the Adverse Event Status Update Case Report Form to document any AE's previously reported as ongoing.

Intra-operative and post-operative complications, whether device-related or not, suspected or not complications will be reported as adverse events. Potential intraoperative and early postoperative complications, related to all total ankle replacements may include:

- a. pain;
- b. sudden drop in blood pressure intra-operatively due to the use of bone cement;
- c. damage to blood vessels;
- d. temporary or permanent nerve damage resulting in pain or numbness of the affected limb;

e. cardiovascular disorders including venous thrombosis, pulmonary embolism, or myocardial infarction.

f. hematoma;

- g. delayed wound healing; and
- h. deep wound infection (early or late) which may necessitate removal of the prosthesis.
- i. rarely an arthrodesis of the involved joint or amputation of the limb may be required.

Potential, late postoperative complications can include:

a. pain;

b. bone fracture by trauma or excessive loading, particularly in the presence of poor bone stock;c. peri-articular calcification or ossification, with or without impediment to joint mobility; andd. inadequate range of motion due to improper selection or positioning of components or periarticular calcification.

Additionally, these complications will be further categorized and reported as device related, or procedure related and outcome.

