Table	4.4.1	Procedure Related Treatment Emergent Adverse Events
Table	4.4.2	Device Related Treatment Emergent Adverse Events
Table	4.5.1	Serious Treatment Emergent Adverse Events
Table	4.5.2	Procedure/Device Related Serious Treatment Emergent Adverse Events

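### The sponsor determines seriousness and device-relatedness, the SAE definition counts either party's view, and the SAP does not say whose call fills the device-related and serious tables

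*Protocol*

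**What the plan says.** **Investigator.** Under Recording and Reporting Adverse Events - Investigator Responsibilities, the protocol has the investigator "Record protocol required AE's together with an assessment as recorded in the Adverse Event Case Report Forms". It does not list what that assessment contains.

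**Sponsor.** The matching section on sponsor responsibilities states that "Wright Medical is responsible for the classification of AEs and ongoing safety evaluation of the study". The sponsor reviews the investigator's assessment of every event and is then to "determine and document, in writing, the seriousness of the adverse event and relationship of the adverse event to the implanted components". If the two disagree, it must "communicate both opinions to concerned parties" and, as required, see that ethics committees and authorities are informed.

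**SAE definition.** Under Serious Adverse Event (SAE), the protocol treats an event as serious "if, in the view of either the investigator or sponsor, it results in any of the following outcomes".

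**SAP.** The adverse event section says that "these complications will be further categorized and reported as device related, or procedure related and outcome". The SAE section plans a separate table and lists criteria taken from ISO 14155:2011. The Listing of Tables includes Table 4.4.2, "Device Related Treatment Emergent Adverse Events", with Table 4.4.1 for procedure-related events, Table 4.5.1 for serious events and Table 4.5.2 for serious events related to procedure or device. None of these places says whose classification is used.

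**The concern.** Two protocol rules give different answers when the investigator calls an event serious and the sponsor does not. For device-relatedness there is no either-party rule at all, only the sponsor's determination. A programmer building the tables needs one value per event. The only text that assigns responsibility for classification assigns it to the sponsor, so that is the likely default.

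The study is non-randomized and describes no comparator group, so no control arm would expose a shift in classification. The party making the determination has an interest in the result. Safety of the implant is a stated secondary objective, and the protocol's Study Rationale says results will be reported to regulatory authorities and notified bodies. A reader of Tables 4.4.2, 4.5.1 and 4.5.2 could not tell whose judgement they show, or whether the parties had differed.

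**Working it through.** The plan attaches no figure to this point, so the check compares the rules and adds one line of arithmetic.

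**Step 1. Seriousness: the four possible combinations.**

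| Investigator | Sponsor | Under the SAE definition (either view) | Under the sponsor's determination |
|---|---|---|---|
| Serious | Serious | Serious | Serious |
| Not serious | Serious | Serious | Serious |
| Serious | Not serious | **Serious** | **Not serious** |
| Not serious | Not serious | Not serious | Not serious |

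The rules differ in one row only, and always in the same direction. A table built on the sponsor's determination can never contain more serious events than one built on the SAE definition.

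**Step 2. Device-relatedness.** The same comparison applies, except that the protocol states no either-party rule here. A sponsor-only count can never exceed an either-party count. It may be above or below an investigator-only count, because the sponsor may also add events.

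**Step 3. Does the disagreement clause settle the matter?** No. It says who must be told of the two opinions, not which opinion is tabulated.

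**Step 4. Does the SAP settle it?** No. The adverse event section, the SAE section and the Listing of Tables name no assessor, and the SAE section does not carry over the either-view wording.

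**Step 5. Which tables could be affected, if the sponsor's determination feeds them?**

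- Investigator says device-related, sponsor says not: the event may be missing from Table 4.4.2. If serious, it may also be missing from Table 4.5.2, unless it is classified as procedure-related as well. It stays in Table 4.5.1.
- Investigator says serious, sponsor says not: the event may be missing from Tables 4.5.1 and 4.5.2.
- In both cases the event remains in the all-event tables (4.1 to 4.3) and in Listing 14.
- The sponsor's stated determination concerns relationship to the implanted components, so the text does not directly govern Table 4.4.1.

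**Step 6. Size per subject.** Inputs: 155 subjects (SAP, Study Design, Overview), taken as the denominator because the safety analysis covers all enrolled and implanted subjects. The number of disagreements is not given; 1 to 5 subjects is an assumed range.

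Fall in subject rate = (subjects whose only device-related event is reclassified) / 155.

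- 1 subject: 1/155 = 0.0065, or 0.65 percentage points.
- 5 subjects: 5/155 = 0.032, or 3.2 percentage points.

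**The case against.** The strongest reply is that nothing in the documents removes an event from a table. The sponsor's determination can be read as a written record of its own view, which is one of the two views the SAE definition counts. On that reading an event the investigator calls serious stays serious, and the sections are compatible. This has some force: loss from the tables is the likely default given the SAP's silence, not a stated rule. It does not remove the need to say which reading applies.

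A reader might also infer three stronger things that the documents do not support.

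- *That the manufacturer classifies events alone.* The investigator records an assessment, the sponsor reviews it, and both opinions are communicated on disagreement. What is missing is independent adjudication and a tabulation rule.
- *That a reclassified event disappears without trace.* The determination must be in writing, and the event stays in the all-event tables and Listing 14. Implant problems also reach the report through secondary surgical interventions, tabulated by reason, and through the radiographic findings. What may be lost is visibility in the device-related and serious tables.
- *That the device-related event rate is the study's main safety figure.* No passage ranks it first or attaches a test or threshold to it. The primary endpoint is survivorship.

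Finally, no document reports or predicts any disagreement. That is true, and it is why the size is given only per subject.

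**Conclusion.** The point holds as a conflict between two protocol rules combined with an unspecified analysis rule. The SAE definition and the sponsor's determination disagree whenever only the investigator calls an event serious, and the SAP does not say which feeds Tables 4.5.1 and 4.5.2. For device-relatedness, the sponsor's determination is the only classification rule available for Tables 4.4.2 and 4.5.2.

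Each subject whose only device-related event is reclassified as unrelated lowers the device-related subject rate by 0.65 percentage points. This rests on a denominator of 155 and on the sponsor's determination being the one tabulated. The total effect cannot be estimated from the documents, and they give no ground for saying that reclassification has happened or will happen. Nothing here alters how the survivorship endpoint is defined. The matter should be settled before the safety tables are produced.

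**What to change.** **SAP.** Add to the adverse event and SAE sections, and apply to Tables 4.4.2, 4.5.1 and 4.5.2: *An event is counted as serious or device-related if either the investigator or the sponsor classifies it so; the number and direction of disagreements are footnoted and flagged in Listing 14.* Use the same rule for procedure-relatedness in Tables 4.4.1 and 4.5.2, for consistency. This extends to relatedness the principle the protocol already uses for seriousness.

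**Protocol.** Reconcile the sponsor-responsibilities section with the SAE definition at the next amendment. The SAP change closes the tabulation gap without it.

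**Check first.** Confirm that the adverse event form captures the investigator's own view of seriousness and relatedness. The protocol does not spell this out. The investigator SAE section treats a change in causality as reportable follow-up, which suggests that causality is recorded at least for SAEs, but not by whom.

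**Cost.** SAP wording and a disagreement flag, if both assessments are held as data; otherwise the missing field must be dealt with. Any protocol change needs ethics approval before implementation. Reported device-related and serious rates may be slightly higher. Naming a single assessor or tabulating both views would also remove the ambiguity, but a single-assessor rule for seriousness would depart from the protocol's SAE definition.

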#### Recording and Reporting Serious Adverse Events (SAE's) – (Immediately Reportable) Investigator Responsibilities

- The investigator must report the following events to the Sponsor within 24 hours after learning of the event, regardless of relationship to study, using the appropriate SAE reporting form and guidelines;
- The investigator must report new significant follow-up information for these events to the Sponsor within 24 hours after becoming aware of the information. New significant information includes the following:
- New signs or symptoms or a change in the diagnosis.
- Significant new diagnostic test results.
- Change in causality based on new information.
- Change in the event/s outcome, including recovery.
- Additional narrative information on the clinical course of the event.

#### Recording and Reporting Serious Adverse Events (SAE's) – Wright Medical Sponsor Responsibilities

• SAEs must be summarized on the annual report to the IRB/EC/REC

#### Recording and Reporting Unanticipated Adverse Device Effect (UADE)- Wright Medical Sponsor Responsibilities

Definition - An adverse reaction that is both unexpected (not consistent with the applicable product information) and also meets the definition of a Serious Adverse Event/Reaction

• UADEs must be reported to the IRB/EC/REC in accordance with GCP guidelines i.e. 7 or 15 days

#### DATA MANAGEMENT

#### **Overview**

All information will be collected according to the protocol and defined case report forms. Investigator subject records (e.g. medical records, imaging reports, surgical notes or, paper case report form booklets) will be considered source documents for the study. This information will be entered by the site through a website provided by Wright Medical. Data will be received by Wright Medical through the electronic data capture system. The Investigator must allow Wright Medical or its representative's access to the subject files. This access includes inspection of records.

In order to facilitate potential site monitoring visits, the investigator is required to keep records, including the identity of all participating subjects, all original signed Informed Consent Documents, and source documents. These records must be retained by the Investigating site according to local regulations as specified in the Clinical Trial Agreement.

If the Investigator relocates, retires, or for any reason withdraws from the study, Wright Medical should be notified ahead of time. The study records must then be transferred to an acceptable designee (another investigator, institution, or Wright Medical). The investigator must obtain Wright Medical's written permission before disposing of any records.

#### Participant Confidentiality

The study team will ensure that the participants' anonymity is maintained. The participants will be identified only by study number on the electronic CRF. All documents will be stored securely and only accessible by study staff and authorized personnel. To ensure confidentiality, none of the data stored or transferred electronically will contain personal identifiers.

#### Monitoring Plan

There is a need for on-site monitoring before, during, and after the clinical study. The sponsor may determine that remote monitoring (without visiting the site), in conjunction with procedures such as investigator's documented training, meetings, and extensive written guidance or telephone communication, can assure appropriate conduct of the clinical study. With the study data being provided to Wright via the remote electronic data capture system, there is an opportunity to review data in a real time manner at Wright Medical and not only reviewed during an on-site visit. The study will be monitored by Wright Medical or its authorized representatives in accordance with the internal procedures of Wright Medical. The frequency of the visits will be determined by Wright and scheduled early on with at least a minimum of each quarter based on enrollment and the number of active follow-up visits at each site. This may vary based on the enrollment and data collected at the sites, any compliance concerns and need for additional training and oversight.

Prior to study initiation, each clinical study site will be inspected by Wright Medical or its authorized representative. Additionally, each site will have an initiation visit to ensure Investigator(s) and study personnel:

- have the appropriate knowledge, experience, and equipment necessary to comply with the study requirements
- fully understand all aspects of the study including the study protocol and data collection methods
- Fully understand the procedures related to subject selection

Upon study commencement, regular monitoring visits will be conducted to ensure:

- ongoing compliance with the study protocol;
- ongoing compliance with any conditions of approval of the reviewing IRB/EC/REC;
- maintenance of complete study and regulatory records
- continued acceptability of the site's facilities

Source documents and Investigator site files will be reviewed during the monitoring visits, including, but is not limited to:

- reviewing case report forms for accuracy and completeness;
- verifying timely and accurate data collection (in comparison with the source documentation);
- reviewing and resolving missing or inconsistent study data;
- verifying the investigational site maintains all required source documents, supporting medical records, and signed Informed Consent Documents; and
- verifying the investigational site maintains documentation and reports for any AEs

Monitors will evaluate and summarize the results of each visit in a written report that identifies any repeated data problems and providing specific recommendations for the resolution of noted deficiencies.

#### Amendments to Study Protocol

Amendments cannot be made to the study protocol without the written consent of Wright Medical. Additionally, amendments to the study protocol must be approved by the IRB/EC/REC prior to their implementation.

## **Deviations from Study Protocol**

Investigators should not deviate from the study protocol except to deliver emergency care or to eliminate an immediate hazard to the subject. Deviations should be reported by completing the Protocol Deviation Case Report Form. Investigators must report all deviations from the study protocol to Wright Medical or its designated representatives. Additionally, any deviations found during monitoring visits must also be reported to Wright Medical or its designated representatives. All deviations with the potential to affect subject safety, rights, or well-being will also be reported to the IRB/EC/REC as soon as possible; based on the IRB/EC/REC requirements within the jurisdiction with each site.

# **STUDY ETHICS**

## Institutional Review Board/Ethical Review Committee

It is the responsibility of the principal investigator at each participating site to obtain prospective approval of the study protocol, protocol amendments, patient information sheets, Informed Consent documents, and any other

relevant documents, if applicable, from the IRB/EC/REC. All correspondence with the IRB/EC/REC should be retained in the Investigator Master site File. Copies of IRB/EC/REC approvals must be forwarded to Wright Medical or its designated representative prior to enrolling subjects. The Investigator must immediately report to Wright Medical or its designated representative if the IRB/EC/REC withdraws its approval of the study for any reason.

#### Statements of Compliance

This study will be conducted in accordance with 21 CFR Part 11, 50, 54, 56, and the ethical principles originating from the Declaration of Helsinki, GCPs, and in compliance with local regulatory requirements. This study will be registered with ClinicalTrials.gov.

## **Financial Disclosures**

All Investigators must complete, sign and date the Financial Disclosure form prior to their participation in the clinical study. Each Investigator must notify Wright Medical or its designated representative if any relevant changes occur during the course of the study and for one year following the completion of the study. Copies of the Financial Disclosure form for each Investigator will be maintained in the sponsor's investigational files.

## Sponsor Discontinuation Criteria

Wright Medical reserves the right to terminate a non-performing site. Reasons for considering early termination or suspension of an individual site may include, but are not limited to:

- Site non-compliance with study protocol or failure to comply with government or local regulations
- Failure to submit data in a timely manner
- Failure to comply with or act upon findings
- Failure to maintain pace to complete enrollment

Wright Medical reserves the right to discontinue the study at any time and will notify each investigator immediately at the time of such a decision. Formal documentation will be provided to the investigators to notify their IRB/EC/REC, research institutions. After such a decision, the Investigator must contact all participating subjects to notify them of this decision and its impact on their follow-up.

# **STUDY COMPLETION**

#### **Subject Enrollment Completion**

Individual subject enrollment will be considered complete once the subject has completed all of their clinical visits and outcome measurements required by the study protocol. The investigator should then complete the Study Completion Case Report Form.

#### **Study Closeout Activities**

The study will be considered complete once the last subject at the last active site has completed their clinical visits and all outcome measurements required by the study protocol. Additionally, the following activities must be completed at each site before the study is considered complete:

- All essential documents are complete and up to date
- The Investigator has completed and submitted all required case report forms

• Arrangements are made for archiving and record retention

All IRB's/EC/REC's have been notified of the conclusion of the study

# APPENDIX

Instructions for Use (IFU), INFINITYTM Surgical Technique

Case Report Forms

# Abbreviations

AE	Adverse Event
AOS	Ankle Osteoarthritis Score
BMI	Body Mass Index
CFR	Code of Federal Regulations
CDRH	Center for Device Radiological Health
CI	Confidence Interval
COFAS	Canadian Orthopaedic Foot & Ankle Society
CRF	Case Report Form
GCP	Good Clinical Practice
FAOS	Foot and Ankle Outcome Score
ІСН	International Conference on Harmonization
IRB/ERC/REC	Institutional Review Board, Ethical Review Committee, Research
	Ethical Committee
LB	Lower Bound
MedDRA	Medical Dictionary for Regulatory Activities
PROMS	Patient Reported Outcome Measures
PROMIS	Patient Reported Outcome Measurement Information System
QoL	Quality of Life
SAE	Serious Adverse Event
SUSAR	Suspected Unexpected Serious Adverse Reactions
TAR	Total Ankle Replacement
UB	Upper Bound
Vs	Versus
WHO	World Health Organization

